# 4.2 STUDY ENDPOINTS

For the purposes of this study, patients should be evaluated for on-treatment response after 4 weeks, and re-evaluated at 2 or 3 months post RT (the selection of post-RT timepoint for imaging is at physician discretion (either is standard of care; eg if CT is negative a 2 months, no further imaging is required. If disease still present at 2 month CT, a 3 month PET will be obtained, or simply a 3 month PET).

4.2.1 On Treatment response at 4 weeks during RT

Week 4 CT and/or MRI will be loaded into the treatment planning system or other software for volumetric evaluation of tumor size. This will be compared against CT simulation or week 1 CT/CBCT and/or MRI, whichever is larger. The percent response will be calculated.

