#### Endpoint

**Primary Endpoint:** For patients with HPV+ squamous cancer of the oropharynx, fractionation of radiation will be individualized based on their PSI. Response will be measured after 4 weeks of RT as assessed by CT or MRI, as described in section 10.0. Primary objective is to increase the rate of response of  $\geq$  32% at 4 weeks to 63% of patients, above the expected 49%.

[figure not shown]
Population:	Total sample size of 60 patients, which will include men and women $\geq$ 18 years with pathologically (histologically or cytologically) proven diagnosis of HPV+ squamous cell carcinoma of the oropharynx and no evidence of distant metastases. This is a single center study
Phase:	2

Number of Sites 1 enrolling participants:

Study Duration:	~30 months		
Agent :	Proliferation Saturation Index – a measure of the carrying capacity of the patient for the tumor burden. We will use this to select radiotherapy fractionation.		
Description of Study			

Participant Duration: ~33 months

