# 7 STUDY PROCEDURES AND SCHEDULE

#### 7.1 STUDY PROCEDURES/EVALUATIONS

 $PSI = \frac{V_{diagnosis} \times e^{\lambda \Delta t} - V_{treatment}}{V_{diagnosis} \times (e^{\lambda \Delta t} - 1)}$ 

PSI will be calculated according the above formula, where Vdiagnosis is the volume of the tumor at first imaging and Vtreatment is the volume of the tumor at second pretreatment imaging, t is time, and  $\lambda$  is doubling time. Each site of disease will be contoured individually, and PSI calculated. PSI of lymph nodes will have priority over primary site. PSI of the largest lymph node will have priority over smaller lymph nodes. Patients with a PSI  $\leq$  0.75 will be assigned to conventional fractionation group, and PSI > 0.75 will be assigned to the hyperfractionation group (Figure 3).

- Medical history within 90 days of start of treatment, including history, focused physical exam of the head and neck, assessment of performance status, and weight.
- Imaging will consist of pre-treatment CT and/or MRI, with at least 2 exams one week apart. Pre-treatment PET/CT while ideal, is not required. On first day of RT (or within 5 days of starting RT), CT simulation will be repeated. During week 4 of radiotherapy (~fraction 20 for conventionally fractionated patients or ~fraction 40 for hyperfractionation patients, CT simulation and MRI will be repeated. At ~8 weeks after treatment is complete CT of neck or ~12 weeks PET/CT will be performed for response assessment.

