# 7.3 STUDY SCHEDULE

		On Treatment					
Assessments	Pre-Study (within 90 d. of Tx start)	First day, prior to RT (within5 days prior)	Once-a- WeekDuring RT	Week 4 During RT	End of Tx (+/- 3 days)		
Evaluations							
Rad Onc EvalH&P, ECOG, Weight	х		Х				
Imaging							
CT# or MRI of primary and neck a,b	Xh	Х		х			
PET/CT	Xc						
Labs							
Urine PregnancyTest (only Females of Child bearing potential)	х						
Tumor Tissue for RSI	Х						
Oral Gargle for HPV e	Х		х	х	х		
Plasma for HPV f	Х		Х	Х	Х		

	From End of Treatment							
Assessments	4 Wks +/- 14 days	2-3 mo +/- 14 days d	6 mo +/- 14 days	12 mo +/- 14 days	18 mo +/- 14 days	24 mo +/- 14 days	Time of disease progression if sooner than 24 mos g	End of study if the patient is off the study before 24 mos with any reasons g
Evaluations								
Rad Onc Eval H&P, ECOG, Weight	х	х	х	Х				

Assessments	4 Wks +/- 14 days	2-3 mo +/- 14 days d	6 mo +/- 14 days	12 mo +/- 14 days	18 mo +/- 14 days	24 mo +/- 14 days	Time of disease progression if sooner than 24 mos g	End of study if the patient is off the study before 24 mos with any reasons g
Imaging								
CT# or MRI of primary and neck a,b		Xc						
PET/CT		Xc						
Labs								
Urine PregnancyTest (only Females of Child bearing potential)								
Tumor Tissue for RSI								
Oral Gargle for HPV e		х	х	х	х	Х	х	Х
Plasma for HPV f		Х	Х	Х	Х	Х	Х	Х

aInterim MRI or CT for response assessment.

bCT at day 1 and week 4 may be done using Department of Radiation Oncology CT SimulationcAt physician discretion. Pre-treatment PET/CT can be up to 180 days prior to CT simulation. dA CT at 2 months and/or PET/CT at 3 months may be done at physician discretion.

eOral Gargle for HPV to be collected at pre-therapy, during treatment at week 1, week 2, week 3, week 4, end of treatment, 3 months post-RT, 6 months post-RT, 12 months post-RT, 18 months post-RT, 24 months post-RT, time of diseaseprogression (if sooner than 24 months), and end of study (if patient discontinues the study with any reason sooner than 24 months). See 7.2.4/7.2.5 for collection windows.

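### The week-4 primary response may be computed across imaging modalities, and no rule says which week-4 volume counts when both CT and MRI exist

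*Combined protocol and SAP*

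**What the plan says.** Four places describe the imaging behind the primary endpoint.

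- **Section 4.2.1.** At week 4: "Week 4 CT and/or MRI will be loaded into the treatment planning system or other software for volumetric evaluation of tumor size". On the comparator: "This will be compared against CT simulation or week 1 CT/CBCT and/or MRI, whichever is larger".
- **Section 7.1.** At the start of treatment: "On first day of RT (or within 5 days of starting RT), CT simulation will be repeated". During week 4, "CT simulation and MRI will be repeated". Pre-treatment imaging may be CT, MRI or both, so a pre-treatment MRI is not mandatory.
- **Section 7.3.** The schedule row reads "CT# or MRI of primary and neck" and is marked at both the first-day and week-4 visits. Footnote a reads "Interim MRI or CT for response assessment". Footnote b permits a CT pair without requiring it: "CT at day 1 and week 4 may be done using Department of Radiation Oncology CT Simulation".
- **Study Summary, Endpoint (and section 3.1 in similar terms).** "Response will be measured after 4 weeks of RT as assessed by CT or MRI, as described in section 10.0". Section 10 contains the hypotheses, bounds and tests, but no rule for measuring response.

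**The concern.** Response is a hard cut, a volume reduction of at least 32%, applied to the ratio of a week-4 volume to a baseline volume. If the two volumes come from modalities that read systematically differently, the difference multiplies that ratio and can carry a patient across the cut with no difference in the tumor. Section 4.2.1 allows this in both directions: MRI at week 4 against CT or CBCT at baseline, or CT at week 4 against MRI at baseline.

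A patient imaged as 7.1 prescribes has both a CT and an MRI volume at week 4, hence two possible response values, and no text says which is the endpoint. The trial is single-arm and describes no blinded or central read. Its decision bounds are one patient wide: 27 against 28 and 29 against 30 of 49, then 34 against 35 of 60.

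The same 32% reduction also governs a treatment change in sections 4.1 and 6.1, so the measurement behind it should be unambiguous there too. No clinical rule is proposed here.

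**Working it through.** **1. The texts side by side**

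| Section | Start of RT | Week 4 | Which volume counts |
|---|---|---|---|
| 4.2.1 | CT simulation, or week 1 CT/CBCT and/or MRI; the larger | CT and/or MRI | not stated |
| 7.1 | CT simulation | CT simulation and MRI | not stated |
| 7.3 | CT or MRI | CT or MRI | not stated |
| 10 | none | none | not stated |

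Sections 7.1 and 7.3 cannot both describe the week-4 requirement. Under 7.1 the week-4 MRI has no expressly required MRI at the start of RT. Under 7.3 a patient may have CT at one visit and MRI at the other.

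**2. The plan's own figures**

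Inputs from section 10.2.1: 49 then 11 more patients; stop at 27 or fewer, or at 30 or more, of 49; reject at 35 or more of 60; p0 = 0.49, p1 = 0.63.

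P(reject) = P(X1 ≥ 30 | 49) + Σ over x = 28, 29 of P(X1 = x) · P(X2 ≥ 35 − x | 11).

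- At 0.49: 0.0580 + 0.0151 + 0.0196 = 0.0928 (stated limit 0.1).
- At 0.63: 0.6611 + 0.0495 + 0.0809 = 0.7915 (stated about 79%).

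The design arithmetic reproduces and is not at fault.

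**3. What an offset does to the cut**

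Let f be the ratio of the week-4 modality's reading to the baseline modality's reading for the same volume. The true reduction that scores as 32% is 1 − 0.68/f.

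- f = 0.90: 1 − 0.68/0.90 = 24.4%.
- f = 1.10: 1 − 0.68/1.10 = 38.2%.

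Illustration: a baseline CT of 10.0 cc and a week-4 CT of 7.5 cc give a 25% reduction, a non-responder. A week-4 MRI reading 10% lower, 6.75 cc, gives 32.5%, a responder.

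**4. Effect on the trial's decision (illustrative)**

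Assumptions, none taken from the documents: true reductions are normal with SD 12, 15 or 20 points, centred so that 49% reach 32%; the offset is 10%; one quarter of patients are scored across modalities. The pooled rate is 0.75 × 0.49 + 0.25 × (rate under the shifted cut), put through the formula in step 2.

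| SD | Rate if under-read | Rate if over-read | Pooled, under | P(reject) | Pooled, over | P(reject) | Pooled, half each way | P(reject) |
|---|---|---|---|---|---|---|---|---|
| 12 | 72.7% | 29.5% | 54.9% | 0.33 | 44.1% | 0.02 | 49.5% | 0.11 |
| 15 | 68.4% | 33.1% | 53.8% | 0.28 | 45.0% | 0.03 | 49.4% | 0.10 |
| 20 | 63.8% | 36.9% | 52.7% | 0.22 | 46.0% | 0.04 | 49.3% | 0.10 |

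A consistent under-read at week 4 raises the chance of a false positive, a consistent over-read lowers it, and balanced offsets leave it close to the design value of 0.093.

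**The case against.** The strongest reply is that the main path already yields a CT pair. Section 7.1 repeats CT simulation at the start of RT and at week 4, footnote b of 7.3 names CT simulation for both, and 4.2.1 lists CT simulation first. Section 6.5 asks for MRI and/or PET/CT to be fused to the planning CT, and 7.1 speaks of MRI being repeated. MRI may therefore be meant as a contouring aid on a registered CT rather than as a rival volume. The # mark on CT in the 7.3 row has no note in the available text, so a clarifying line may have been lost.

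Much of this stands. Cross-modality scoring is possible, not shown to happen, and its frequency is unknown. But no passage requires the CT pair, and 4.2.1 expressly admits other pairs.

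Three stronger readings are tempting, and the documents support none of them:

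- **That the type I error is inflated.** No CT–MRI or CT–CBCT offset, direction or frequency is documented; inflation needs an offset that runs consistently one way.
- **That an offset alone can make any patient a responder.** At a 10% under-read, only true reductions between 24.4% and 32% cross the cut; a patient with no change would need a 32% offset.
- **That the favourable week-4 scan will be chosen.** The text is silent on the choice; it provides for no such selection.

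**Conclusion.** The gap in the endpoint definition is established by the text: a cross-modality response is permitted, two week-4 volumes may compete, and 7.1 and 7.3 need reconciling. Confidence in that is high.

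The effect on the trial's conclusion is not established. The range of 0.02 to 0.33 around a design value of 0.093 is conditional on an assumed 10% offset, an assumed one-quarter share and an assumed normal spread. It shows that the rule could matter in either direction, including hiding a real effect, and not that the result is biased upward. Since the null rate of 49% puts the cut near the median reduction, many patients may lie close to it.

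The point should be corrected because the remedy is cheap, and it is best handled as one item with the larger-baseline rule in the same paragraph of 4.2.1. The two share a source, and their effects should not be added.

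**What to change.** 1. In 4.2.1, prespecify one same-modality pair for the same lesion or lesions in every patient. The default would be the start-of-RT CT simulation (day 1, within 5 days) against the week-4 CT simulation. Name that scan explicitly, because the planning CT simulation is a second pre-RT candidate.
2. Remove CBCT and cross-modality pairs from the primary endpoint, and settle the larger-baseline rule in the same edit.
3. Report MRI-to-MRI change as a sensitivity analysis where both MRIs exist.
4. Reconcile the Study Summary endpoint and sections 3.1, 4.2.1, 7.1 and 7.3, and either place the rule in section 10 or correct the cross-reference to it.
5. Confirm which modality and baseline lie behind the 32% cut and the 49% historical rate, which the documents do not state. Match the chosen pair to that method or declare the mismatch.

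Cost: wording only. Section 7.1 already schedules CT simulation at both times, so no scans are added, and N, bounds and power are unchanged. The small downside is that MRI no longer enters the primary read.

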# 2.2 PROLIFERATION SATURATION INDEX

Tumors are composites of proliferating and growth arrested cells. Overall radiation response depends on their respective proportions at irradiation. In multi-compartment mathematical models that distinguish between proliferating and growth-arrested cells, we have shown that proliferation and oxygenation status-dependent radiation response can be simulated on the cellular level. Tumor growth in vivo can be approximated by logistic dynamics. Initial exponential growth at low cell densities when most cells have access to ample resources decelerates when cells at the core of the tumor become growth-arrested, mainly due to limited space and exhausted intratumoral nutrient supply as resources are consumed by cells closer to the tumor surface. This established the notion of a tumor carrying capacity (K) as the maximum tumor volume that can be supported by a given environment. The tumor carrying capacity is patient-specific, depending on the established oxygen and nutrients supply through tissue vascularization, removal of metabolic waste products, and evasion of immune surveillance. Hence, the tumor volume-to-carrying capacity ratio (V/K) describes the saturation in overall tumor cell proliferation as the tumor approaches its carrying capacity, which we call a Proliferation Saturation Index (PSI). Logistic

growth is modeled as  $dt = T_{POT}$  (eqn. 1), where V is the tumor volume at time t, dV/dt is the change of tumor volume over time TPOT is the intrinsic potential doubling time.

Radiation response is modeled as instantaneous volume changes  $V_{postIR} = V - \gamma_d V(1 - PSI)$  (eqn. 2)

**Figure 1. A)** Two patients with identical tumor volume but different PSI at treatment begin (day 0) exhibit different reduction in tumor volume after fractionated RT. **B**) Logistic tumor growth and radiation response model predicted curves (*eqns.* 1+2; solid black lines) to four lung cancer patientsdata (red circles) with growth rate  $ln2/T_{POT}=0.045$  and radiation-induced death  $\gamma_{2Gy}=0.084$ , and patient-specific carrying capacities Ki. PSIi: Proliferation Saturation Index for patient Pi at first treatment (t=0).

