Additionally, recent review of Moffitt Cancer Center internal data suggests that patients with greater than 5 positive lymph nodes are at a higher risk of regional failure, with locoregional control at 3 years of 94.9% for 1-5 lymph nodes vs 80.1% for > 5 lymph nodes (p = 0.001). By restricting patients to T1-2 N0-1 with 5 or less lymph nodes and a smoking history of 10 pack years or less, 3-year locoregional control of patients treated with radiation alone at Moffitt Cancer Center was 94.7% (n=81) compared to 95.9% with concurrent radiotherapy and systemic therapy (n=98) (personal communication [name]).

In a retrospective analysis of 44 patients, decrease in nodal size of  $\geq$  40% was associated with a locoregional control (LRC) of 100% at 2 years, compared with 78% for a decrease of < 40%. Retrospective review of a Moffitt cohort (n=49) suggests that a cut point of 32% reduction resulted in 100% LRC and DFS (Figure 2A&B). Of note, half of these patients were treated with radiation alone.

In the mathematical modeling of radiation treatment response, there is a suggestion of a more robust treatment response by hyperfractionation when the PSI is > 0.75 (Figure 3).

[figure not shown]

Figure 3: Model of tumor response at 4 weeks by initial pretreatment PSI.

We therefore hypothesize that by personalizing the fractionation, we will increase the number of patients achieving a 32% reduction by week 4.

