#### **3 OBJECTIVES AND PURPOSE**

#### 3.1 PRIMARY OBJECTIVE

For patients with HPV+ squamous cancer of the oropharynx, fractionation of radiation will be individualized based on their PSI. Response will be measured after 20 days of RT as assessed by CT or MRI, as described in section 10.0. Primary objective is to increase the rate of response of  $\geq$  32% at 20 days to 63% of patients, above the expected 49%.

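### Week-4 shrinkage is scored against the larger of two baseline scans but tested against a fixed 49% whose baseline scan is not stated, so the 0.10 type I error cannot be confirmed

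*Combined protocol and SAP*

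**What the plan says.** Section 4.2.1 defines the on-treatment response. The week-4 CT and/or MRI is measured volumetrically, and "This will be compared against CT simulation or week 1 CT/CBCT and/or MRI, whichever is larger". Two baseline volumes will be routine, because section 7.1 adds a scan at the start of treatment: "On first day of RT (or within 5 days of starting RT), CT simulation will be repeated". The section 7.3 schedule places this scan before radiotherapy ("First day, prior to RT (within5 days prior").

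A responder has a reduction of at least 32%. Section 10.2.1 tests the responder rate, one-sided, against a historical 49%, in a two-stage design with a type I error of 0.1 and about 79% power at 63%.

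On how response is measured, section 3.1 points elsewhere: "Response will be measured after 20 days of RT as assessed by CT or MRI, as described in section 10.0". Section 10 gives the test, the stopping bounds and the confidence interval. It gives no baseline rule for the trial or for the control, and no sensitivity analysis on the choice of baseline.

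Sections 3.1 and 10.2.1 cite the 49% to reference 11, whose title concerns nodal response. Section 2.3 cites the same reference for the 32% cut point: "Retrospective review of a Moffitt cohort (n=49) suggests that a cut point of 32% reduction resulted in 100% LRC and DFS". It does not say which scan served as baseline in that cohort, in which modality, or for which lesion.

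**The concern.** In a single-arm trial the fixed 49% carries the whole comparison, so the trial and the control should measure the endpoint in the same way. Taking the larger of two noisy volumes is not neutral: part of the apparent shrinkage is then the upward error in whichever baseline read higher. Real growth between planning and the start of treatment would add to this, and growth is part of the trial's own model (section 2.2: "Tumor growth in vivo can be approximated by logistic dynamics").

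If the control was scored on one of those scans alone, a treatment with no advantage would show a response rate somewhat above 49% simply because of the scoring rule. The trial could then be called promising more often than the stated error rate allows. From the document alone, a reader cannot tell whether this applies.

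**Working it through.** **Inputs.** From 10.2.1: null rate 0.49; alternative 0.63; 49 patients, then 11 more; stop for futility at 27 or fewer responders, stop for efficacy at 30 or more; final success at 35 or more of 60. From 4.2.1: the larger-of-two baseline. The document gives no scan measurement error, so step 4 rests on assumptions.

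**1. Reproduce the plan's figures.** The probability of declaring success at true rate p is

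P(X1 ≥ 30) + P(X1 = 28)·P(X2 ≥ 7) + P(X1 = 29)·P(X2 ≥ 6), with X1 ~ Bin(49, p) and X2 ~ Bin(11, p).

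- p = 0.49: 0.0580 + 0.0597 × 0.2523 + 0.0415 × 0.4729 = 0.0580 + 0.0347 = 0.0928 (rounded from unrounded terms).
- p = 0.63: 0.6611 + 0.0804 × 0.6150 + 0.0992 × 0.8153 = 0.6611 + 0.1303 = 0.7915 (likewise).

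This agrees with the stated 79% power, and with 0.1 as a ceiling on type I error.

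**2. Direction.** Let A and B be the two baseline volumes and W the week-4 volume. Since max(A, B) ≥ A and max(A, B) ≥ B, the reduction 1 − W/max(A, B) is at least 1 − W/A and at least 1 − W/B. Relative to either scan alone, a patient can become a responder and cannot stop being one. For example, response requires W ≤ 0.68 × baseline. If B is 5% larger than A, this becomes W ≤ 0.68 × 1.05 × A = 0.714 A, so a 28.6% reduction on scan A is enough.

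**3. How much lift the design tolerates.** Using the formula in step 1:

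| True null rate under the trial's scoring | Type I error |
|---|---|
| 0.49 | 0.0928 |
| 0.4928 | 0.100 |
| 0.50 | 0.120 |
| 0.51 | 0.153 |
| 0.52 | 0.192 |
| 0.54 | 0.284 |

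The margin is 0.4928 − 0.49 = 0.28 percentage points. For scale, one patient in a cohort of 49 is 1/49 = 2.0 points.

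**4. Illustration of the possible lift.** Assumptions: the control used one of the two scans; scan errors are log-normal with a CV of 5% or 10%; the true log volume ratio is normal with SD 0.25, 0.35 or 0.50; the two baseline errors have correlation ρ; there is no systematic difference between the scans. The mean log ratio is set so that the single baseline gives 49%. The response rate is then recomputed with the larger baseline and put through step 1. Type I error, for SD 0.25 / 0.35 / 0.50:

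| ρ | CV 5% | CV 10% |
|---|---|---|
| 0 | 0.252 / 0.198 / 0.162 | 0.448 / 0.337 / 0.251 |
| 0.5 | 0.194 / 0.162 / 0.139 | 0.314 / 0.246 / 0.194 |
| 0.8 | 0.151 / 0.133 / 0.120 | 0.213 / 0.178 / 0.151 |
| 0.95 | 0.119 / 0.112 / 0.106 | 0.145 / 0.131 / 0.119 |

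The range is about 0.11 to 0.45. A control scored by the same larger-of-two rule gives 0.093 whatever the measurement error.

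**The case against.** The strongest reply is that no mismatch has been shown. The control comes from the trial's own centre and may have been scored by the same rule; type I error would then be 0.093. This stands: the document supports only that the control's baseline is not stated.

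The direction in step 2 holds only against one of the two scans named in 4.2.1. Suppose the control used a different, earlier scan that read 5% (log) larger, and keep the other assumptions of step 4. Type I error is then about 0.010 to 0.12, mostly below 0.10. Growth would usually make an earlier scan smaller, but the document does not settle the matter. A reader might infer that the rule always favours a promising result; that does not follow.

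Other differences from the control may pull the opposite way. Section 2.3 says of the cohort: "Of note, half of these patients were treated with radiation alone". Section 6.5 of the trial bars concurrent chemotherapy. If systemic therapy raised the 49% and the trial's true null rate were 0.47, type I error would be 0.052. The 49% is itself imprecise: if it is 24 of the 49 patients in that cohort, its exact 95% interval is 34% to 64%. The net bias is therefore unknown. These points limit what can be claimed about the trial's overall error rate, but they do not justify leaving the baseline of the comparator undefined.

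Finally, measurement error, spread and correlation are all assumed in step 4. That also stands. Only the direction relative to the two named scans and the 0.493 threshold are free of those assumptions.

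**Conclusion.** The concern holds in conditional form. The larger-of-two rule can raise, and never lowers, the responder count relative to either named scan alone. If the 49% came from one of those scans, then, all else equal, type I error passes 0.10 once the rule lifts the null rate above about 49.3%, and it is 0.153 at 51%. With the same rule in the control it stays at 0.093. With a different, earlier scan the direction is not established. The document does not show which case applies.

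A reader might infer that the trial's type I error is in fact inflated, or take the 0.11 to 0.45 range as an estimate. Neither is supported: the first needs the control's scoring rule, and the second rests on assumed error. A reader might also infer that a promising conclusion should depend on a single-baseline result. That goes too far for an unverified mismatch. If the control itself used larger-of-two and the trial were judged on the planning scan, the step 4 assumptions plus 5% (log) growth between scans would bring power from 0.79 down to about 0.16 in the worst case.

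The point should be addressed, because the margin is small and the clarification is cheap. Confidence is medium.

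**What to change.** 1. In 10.2.1, state the scan, modality and lesion that produced the 49%. In 4.2.1, use that same baseline for the primary test. If the cohort was scored by larger-of-two, the present rule can stay, and the text should say so.
2. Pre-specify a sensitivity analysis of the week-4 response rate using one fixed pre-RT baseline, the planning CT simulation, and the same modality at week 4 where available. Report it beside the larger-of-two result. Section 7.1 states that at week 4 "CT simulation and MRI will be repeated", but 4.2.1 and the 7.3 schedule allow CT or MRI alone, so a match will not exist for every patient.
3. Optionally, re-derive the 49% under the trial's rule. This is possible only if the cohort's patients have two baseline scans, which the document does not show.

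Cost: one sentence in 10.2.1, a wording change in 4.2.1 and a small extra analysis, with no new visits. The reported response rate may be slightly lower under a single baseline.
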